11.3 Pharmacokinetic and Other Secondary Analyses

11.3.1 List of Tables

Table 21 Summary of pharmacokinetic parameters by injection

Table 22 Assess the time to steady state of the plasma drug concentration, C_{τ}

Table 23 Associations of sex at birth (or BMI) with pharmacokinetic parameters

Table 24 Change in sexual risk behavior (number of sexual partners) from baseline

Table 25 HIV incidences during the study

Table 26 Reported pregnancies by treatment arm and cohort

Table 27 The proportion of women experiencing any Grade 2 or higher AEs (a) prior to completion of the full oral phase and (b) prior to completion of the full injection phase --- among the women who use any injectable hormonal contraception (combined cohort)

Table 28 The proportion of the women who discontinue the study product for reasons of toxicity, tolerability, or acceptability (a) prior to completion of the full oral phase and (b) prior to completion of the full injection phase—among the women who use any injectable hormonal contraception

Table 29 Summary of pharmacokinetic parameters by injection and cohort —among the women who use any injectable hormonal contraception

11.3.2 List of Figures

Figure 8 Plot of plasma CAB concentration over time by cohort

Figure 9 Percentage of participants who experienced ISR by arm, injection and cohort

Figure 10 Plot of change in sexual risk behavior over time from the baseline by treatment arm and cohort

12 ATTACHMENTS

- The tables shell: the tables listed in Section 11.
- The figures shell: the figures listed in Section 11.

Appendix

Definition of Derived Variables and Study Populations

Study Populations:

Randomized population: randomized=1 if Screnr = 1 (Form SO-1 006, screening outcome)

Oral safety analysis population: randomized=1 and PCpdn>0 and PCpbrp="No", or PCpdn>Pcnumpil if PCpbrp="Yes" (Form PC-1 134, Pill count)

Primary/Injectable safety analysis population: randomized=1 and Iaingiv=1 for week5 (Form IA-1 126, Injection administration)

Derived Variables:

BMI=weight (in kg)/ height(in cm)*height(in cm) (Form LLR-1152, Local Laboratory Results)

Algorithm of defining the phase for AEs

The phase (oral or injection) of AEs was determined based on the AE on-set date and the first injection date as follows.

For AEs with a complete onset date (no missing on day, month, or year)

1. If the AE onset date is before of the first injection date, then the phase of the AE is oral.
2. If the AE onset date is after the first injection date, then phase of the AE is injection.
3. If the AE onset date is on the same date as the first injection date, then:
 - a. If the AE is Injection site reaction, then the phase of the AE is injection.
 - b. If the AE is not Injection site reaction, then the phase is oral.

For the AEs with an incomplete onset date (missing day, day is not mandated)

1. If the onset date is before the first injection date determined by the month and the year of the onset date, then the phase is oral.
2. If the onset date of the AE is after of the first injection date determined by the month and the year of the onset date, then the phase is injection.
3. If the month and year in the AE onset date match to the month and year in the first injection date, then:
 - a. the sites determined whether the AE occurred before or after the first injection.
 - b. If the sites could not determine, PI determined which phase the AE should be.

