4.4 Study Visits

Cohort 1:

- Week 0: enrollment visit
- Weeks 2 and 4: oral phase safety visits
- Week 5: the first injection visit
- Weeks 6, 9, 13: safety visits after the 1st injection
- Week 17: the second injection visit
- Weeks 18 and 23: safety visits after the 2nd injection
- Week 29: the third injection
- Weeks 30, and 35: safety visits after the 3rd injection
- Week 41: primary endpoint visit
- Weeks 53, 65, 77, 89, 101: tail phase safety visit
- Week 105: final study visit.

Cohort 2:

- Week 0: enrollment visit
- Weeks 2 and 4: oral phase safety visits
- Week 5: the first injection visit
- Week 6: safety visits after the 1st injection
- Week 9: the second injection visit
- Weeks 10 and 13: safety visits after the 2nd injection
- Week 17: the third injection visit
- Weeks 18 and 21: safety visits after the 3rd injection
- Week 25: the forth injection
- Weeks 26, and 29: safety visits after the 4th injection
- Week 33: the fifth injection visit
- Week 34 and 37: safety visits after the 5th injection
- Week 41: primary endpoint visit
- Weeks 53, 65, 77, 89, 101: tail phase safety visit
- Week 109: final study visit.

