6.2 Randomized Population

The Randomized Population will consist of all participants who meet the study criteria and are randomly assigned to a treatment in the study at the enrollment date.

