6.3 Safety Population

The Safety Population will consist of the participants who are enrolled in the study and have received at least one dose of the study product. In the analyses, the participants will be grouped based on the initial randomization assignments regardless how many doses of the study product they have received.

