6.4 Primary/Injectable Safety Population

The Primary/Injectable Safety Population is a subset of the Safety Population that consists of the participants who have received at least one injection of study product. In the analyses, the participants will be grouped based on the initial randomization assignment regardless how many injections they have received.

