9.5.5 Safety Endpoint

Primary safety endpoint is the proportion of participants experiencing any Grade 2 or higher clinical AEs or laboratory abnormalities since the initial injection to 12 weeks (8 weeks) after the last injection in Cohort 1 (Cohort 2) among the participants who complete at least one injection to evaluate the safety of the 744 injectable during the injection phase. A secondary safety endpoint is the proportion of Grade 2 or higher clinical AEs or laboratory abnormalities occurred from the initial injection to 76 weeks in both cohorts after last injection among the participants who complete at least one injection to evaluate the safety of the 744 injectable in long term; the proportion of Grade 2 or higher AEs or laboratory abnormalities occurred during the oral phase (Weeks 0-5) among all enrolled participants to evaluate the safety of the oral 744 product; and the proportion of Grade 2 or higher AEs or laboratory abnormalities occurred during the whole study period among the all enrolled participants to evaluate the safety of the oral and injectable product. The proportions of endpoints and the %95 confidence intervals will be estimated for each treatment arm. The 95% CIs will be estimated using Wilson score method¹. The proportions of endpoints will be compared between the treatment arms using Fisher Exact test.

In addition, the safety endpoint rate might be calculated for each treatment arm and compared between the treatment arms. The safety endpoint rate is the number of the participants who have experienced Grade 2 or higher clinical AEs or laboratory abnormalities during the study period (defined in each safety analysis) divided by the person-time-at-risk throughout the observation period within the study period.

The 95% exact confidence interval of the safety event rate will be calculated for each treatment arm, assuming the rate follows the Poisson distribution. The safety event rate will be compared between the treatment arms using exact Poisson test.

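### The Appendix flags do not reproduce the Section 6 safety populations: the primary flag accepts only a Week 5 injection, and the oral-phase proportion has three denominators

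*SAP*

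**What the plan says.** **Primary set.** SAP Section 6.4 says the Primary/Injectable Safety Population "consists of the participants who have received at least one injection of study product". Sections 3.1 and 9.5.5 (primary safety endpoint) and Sections 3.1 and 9.6 (tolerability) use the same condition. The Appendix turns it into a data flag: "Primary/Injectable safety analysis population: randomized=1 and Iaingiv=1 for week5". Section 4.4 lists, for both cohorts, "Week 5: the first injection visit". The AE-phase algorithm in the same Appendix works from the date of the first injection and not from a visit number.

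**Oral-phase set.** Section 6.3 defines the Safety Population as "participants who are enrolled in the study and have received at least one dose of the study product". Section 9.5.5 takes the Grade 2 or higher proportion "occurred during the oral phase (Weeks 0-5) among all enrolled participants to evaluate the safety of the oral 744 product". The Appendix has a third rule, beginning "Oral safety analysis population: randomized=1 and PCpdn>0 and". It continues with one branch for PCpbrp = No and, after an or, a second branch for PCpbrp = Yes that compares PCpdn with Pcnumpil.

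**Which governs.** Sections 9 and 9.5 say that analyses use the populations set out in Section 6.

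**The concern.** The Appendix is what a programmer will code. If its flags select different people from the text, the reported denominators are not those the plan defines, and the outcome depends on which page was followed.

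For the primary flag, the denominators of both primary endpoints are at stake. A participant whose first injection sits under a visit other than Week 5 would have AEs assigned to the injection phase by first injection date, yet would be absent from the injectable population.

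For the oral rule, a secondary safety proportion is at stake. Leaving before tablets are counted may be related to an oral AE, so a rule that loses people with no pill-count record cannot be assumed to lose them at random.

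**Working it through.** The SAP states no figure on this point, so there is none to reproduce. The check compares the rules case by case and then sizes the effect of one misplaced participant.

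**1. Primary flag against Section 6.4** (participants with randomized = 1)

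| Injection recorded at Week 5 | Injection recorded later | Section 6.4 | Appendix flag |
|---|---|---|---|
| yes | yes or no | in | in |
| no | yes | in | **out** |
| no | no | out | out |

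The rules differ in one row only. If every first injection is recorded under Week 5, that row is empty and the two sets are identical.

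**2. Oral-phase denominators.** This reads the variables by name, which is an assumption because the form is not shown: PCpdn as tablets dispensed, PCpbrp as whether tablets were brought back, Pcnumpil as the number brought back.

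| Participant | 6.3 | 9.5.5 | Appendix |
|---|---|---|---|
| tablets brought back, some taken | in | in | in |
| tablets brought back, none taken | out | in | out |
| nothing brought back, some taken | in | in | in |
| nothing brought back, none taken | out | in | **in** |
| no pill-count record, some taken | in | in | **out** |

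With no record, PCpbrp is neither No nor Yes, so neither branch is met. If tablets came back but the count is blank, the rule does not say what to do, and the result depends on how the program treats the blank.

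Without brackets, the condition can be read as (randomized = 1 and PCpdn > 0 and No) or (PCpdn > Pcnumpil and Yes). On that reading the second branch does not require randomized = 1.

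**3. Size of one lost participant.** Arm sizes are from Section 2.4: 82 and 28 randomized in Cohort 1, about 66 and 22 planned in Cohort 2. These are not counts of injected participants. Event rates of about 30%, 60% and 90% are assumed. With x events among n and p = x/n:

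- dropping one participant with an event: (x−1)/(n−1) − x/n = −(1−p)/(n−1)
- dropping one participant without an event: x/(n−1) − x/n = p/(n−1)

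Example, n = 28 and x = 17: 16/27 − 17/28 = 59.3% − 60.7%, a change of −1.5 points after rounding.

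| n | x at about 30 / 60 / 90% | with event (points) | without event (points) |
|---|---|---|---|
| 82 | 25 / 49 / 74 | −0.9 / −0.5 / −0.1 | +0.4 / +0.7 / +1.1 |
| 66 | 20 / 40 / 59 | −1.1 / −0.6 / −0.2 | +0.5 / +0.9 / +1.4 |
| 28 | 8 / 17 / 25 | −2.6 / −1.5 / −0.4 | +1.1 / +2.2 / +3.3 |
| 22 | 7 / 13 / 20 | −3.2 / −1.9 / −0.4 | +1.5 / +2.8 / +4.3 |

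Losing three participants from a placebo arm could move it by up to about 11 points. For example, with n = 22 and x = 7, dropping three with events gives 4/19 − 7/22 = −10.8 points.

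**The case against.** The strongest defence is that the SAP treats Week 5 and the first injection as the same thing. Section 7.1 ends the oral phase at the first injection, labelled Week 5, and starts every injection window there. Section 4.5 codes out-of-window visits as late or early, which suggests that a delayed Week 5 visit stays a Week 5 visit. Product holds appear in Section 10.1.1 only as a line in a by-site table, and nothing there describes a first injection under a later visit. This stands as a reason to expect few cases or none. It does not remove the mismatch: Section 4.5 leaves rescheduling to case-by-case consultation, no passage excludes a later first injection, and the flag is narrower than the sections it implements.

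On the oral rule, the form's coding is not shown. If sites enter No for someone who left before any count, that person is included. This also stands, but the written rule does not say so. The loose bracketing may be harmless in practice, since someone with a pill count would normally have been randomized.

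A reader might infer four stronger points that the SAP does not support:

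- *That the primary set inherits an eligibility condition.* Section 6.2 limits its population to "all participants who meet the study criteria and are randomly assigned to a treatment in the study at the enrollment date", but the Appendix sets randomized = 1 from Screnr = 1 on the screening-outcome form and tests nothing else. Sections 6.3 and 6.4 do not mention eligibility. An exclusion appears only if the wording of 6.2 replaces the coded flag.
- *That Section 9.5.5 drops dosed participants.* Its primary denominator agrees with 6.4. Its oral denominator is wider than 6.3, so it can add undosed participants but loses nobody.
- *That pill-count losses bias the primary endpoints.* Someone who leaves before the first count is not injected, and the primary flag does not depend on the oral one.
- *That one participant shifts a proportion by 1/n, or 3.6 points at n = 28.* A dropped participant leaves the denominator too. At a rate of about 60%, dropping one with an event gives 1.5 points.

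**Conclusion.** The point holds as a mismatch between coded and stated populations. The primary flag is narrower than Section 6.4, and the oral-phase proportion has three denominators that do not coincide, although Section 9.5 names Section 6 as governing. Omission of dosed participants can come only from the Appendix flags. It needs either a first injection recorded under a later visit (primary endpoints) or a missing pill-count record (secondary oral endpoint).

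The SAP does not show that either occurs, and the number affected may be zero. If one participant were lost, the shift would be small in the active arms (at most 1.1 points at n = 82 and 1.4 at n = 66) and larger in the placebo arms (up to 3.3 points at n = 28 and 4.3 at n = 22). These figures rest on the assumed event rates and on randomized or planned arm sizes. The reason to act is that the rules should agree before the data are unblinded and that the correction is cheap.

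**What to change.** 1. **Appendix, primary flag:** require randomized = 1 and Iaingiv = 1 at any visit. The AE-phase algorithm already works from the first injection date and needs no change.
2. **Section 9.5.5, oral phase:** replace the all-enrolled denominator with the Section 6.3 Safety Population.
3. **Appendix, oral flag:** bracket the condition so that randomized = 1 applies to the whole rule. Include every randomized participant who was dispensed tablets unless zero doses are documented. This also settles the missing pill-count record.

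The cost is SAP wording and two flag definitions, with no new data. One small downside is that a participant who was dispensed tablets and took none, with nothing to document it, stays in the oral denominator.

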3.2 Secondary Objectives and Endpoints

Secondary Objectives

- Evaluate the safety and tolerability of GSK1265744 (daily oral 744 + 744LA) for 76 weeks of follow-up after final injection (each cohort will be analyzed separately)
- Evaluate the safety and tolerability of oral 744 from Week 0 to Week 5

- Evaluate the pharmacokinetics of 744LA administered as 800 mg IM every 12 weeks for 52 weeks of follow-up after final injection
- Evaluate differential pharmacokinetics of 744LA in participants by age, gender, race, ethnicity, weight, body mass index (BMI), and smoking status
- Evaluate the acceptability of 744LA injections
- Evaluate the effect of 744LA on sexual risk behavior by change from enrollment for repeat assessments to during the study period
- Evaluate HIV incidence and antiretroviral drug resistance, if any participants acquire HIV infection during the study
- Evaluate the safety, tolerability and pharmacokinetics of 744LA in the subset of women who use a hormone-based contraceptive

Secondary Endpoints

- Proportion of participants who discontinue either oral or injectable study product for reasons of toxicity, tolerability, or acceptability prior to completion of the full oral and injectable phases
- Proportion of participants experiencing Grade 2 or higher clinical AEs and laboratory abnormalities during 52 weeks following final injection (safety) and any AE that leads to discontinuation (tolerability) during the aggregate oral and injectable phases
- Proportion of participants experiencing Grade 2 or higher clinical AEs and laboratory abnormalities (safety) and any AE that leads to discontinuation (tolerability) in the oral phase and washout period
- Plasma drug levels of GSK1265744 at designated time points after each injection of 744LA (by cohort only)
- Plasma drug levels of GSK1265744 at designated time points after each injection of 744LA stratified by age, gender, race, ethnicity, weight, BMI, and smoking status
- Proportion of participants willing to use an injectable agent such as the study product for HIV prevention in the future
- Change from enrolment of self-reported sexual behaviour (number of sexual partners, episodes of unprotected anal and/or vaginal intercourse) during the study period using a standardized assessment tool (in aggregate only)
- Number of incident HIV infections through the study period, including number with treatment emergent resistance

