9.7.1 Association between Pharmacokinetics and Baseline Characteristics

To evaluate differential pharmacokinetics of 744LA in participants by age, gender, race, ethnicity, weight, body mass index (BMI), and smoking status, we will use GEE regression model to account the correlations of the PK parameters following three injections in Cohort 1 or five injections in Cohort 2. The analysis will be performed separately for each cohort. The associations between the PK parameters and the predictors will be tested in univariate models (include one predictor in each model) and

in a multivariate model (include all predictors). Each model will be adjusted for sites (US vs. Non-US sites) by cohort.

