10.2 Safety Tables and Graphs (SMC Close Report)

10.2.1 List of Tables

- Permanent discontinuation of study regimen during the oral phase (Weeks 0-5) by treatment arm
- Permanent discontinuation of study regimen during the injection phase (Weeks 5-41) by treatment arm
- Permanent discontinuation of study regimen during the tail phase (Weeks 41-105/109) by treatment arm
- List of early discontinuation of study regimen (reason, study week)
- Grade 3 or higher adverse events by treatment arm during the oral phase (Weeks 0-5)
- Proportion of Grade 2 or higher adverse events by treatment arm during the oral phase (Weeks 0-5)
- Adverse events by severity and relationship to study product during the oral phase (Weeks 0-5)

- Adverse events by MedDRA preferred term ordered by system organ class during the oral phase by treatment arm (Weeks 0-5)
- listing of Grade 3 or above adverse events during the oral phase by treatment arm (Weeks 0-5) with details of the events including severity, relationship to the study product, on-set date, outcome, duration, the enrollment date and days since the enrollment.
- Grade 1 or above AST/ALT by treatment arm during the oral phase (Weeks 0-5)
- Grade 2 or higher adverse events by treatment arm during the injection phase (Weeks 5-41)
- Number and percentage of adverse events by severity and relationship to study product during the injection phase (Weeks 5-41)
- Adverse events by MedDRA preferred term ordered by system organ class during the injection phase (Weeks 5-41)
- Injection site reaction (ISR) adverse events during the injection phase by BMI (above/below median BMI) (Weeks 5-41)
- Grade 1 or above AST/ALT by treatment arm during the injection phase (Weeks 5-41)
- Adverse events by MedDRA preferred term ordered by system organ class during the injection phase (Weeks 5-105/109)
- listing of Grade 3 or above adverse events during the whole injection phase (Weeks 5-81) with details of the events including severity, relationship to the study product, on-set date, outcome, duration, last injection date, and the number of injections prior to the event
- Adverse events by severity and relationship to study product and treatment arm during the whole injection phase (Weeks 5-105/109)
- Grade 1 or above AST/ALT by treatment arm during the whole injection phase (Weeks 5-105/109)
- HIV infection status by study arm
-

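### The appendix formula for BMI does not give BMI under either reading: left to right it returns body weight, and with the product as denominator it is 10,000 times too small; no primary endpoint is affected

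*SAP*

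**What the plan says.** The Appendix, under Derived Variables, gives one formula, tied to the local laboratory results form: "BMI=weight (in kg)/ height(in cm)*height(in cm". The brackets in that line enclose unit labels only; none groups the two heights. Height is given in centimetres both times, and there is no conversion factor. Nowhere else does the SAP give a BMI formula, a unit for BMI or a BMI cut-off.

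BMI is used in these places:

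- **Section 3.2**, secondary PK endpoint: drug levels are to be reported "stratified by age, gender, race, ethnicity, weight, BMI, and smoking status". Weight and BMI are separate factors.
- **Section 9.7.1**: PK parameters are compared "by age, gender, race, ethnicity, weight, body mass index (BMI), and smoking status, we will use GEE regression model", one predictor at a time and then "in a multivariate model (include all predictors". Weight and BMI therefore stand in the same model.
- **Section 9.13**: BMI is among the demographic variables that may be explored against PK.
- **Section 10.2.1**, SMC closed report: injection site reactions are tabulated "by BMI (above/below median BMI".
- **Section 11.3.1**, Table 23: "Associations of sex at birth (or BMI) with pharmacokinetic parameters".

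Section 9.1 names SAS for the primary endpoints and SAS and/or R for everything else.

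**The concern.** BMI is weight in kilograms divided by the square of height in metres. The printed line departs from this in two ways: the squared height is not bracketed, and height stays in centimetres. The same Appendix defines the analysis populations by form fields and conditions, so a programmer, or a second programmer validating the first, has reason to treat the line as a specification.

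At stake are a covariate in a secondary PK objective, the grouping variable of one SMC safety table, and the BMI part of one final-report table. How much harm follows depends on which of two readings is programmed, so they have to be kept apart.

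**Working it through.** **Inputs.** The formula is from the Appendix and its uses from sections 3.2, 9.7.1, 10.2.1 and 11.3.1. The SAP states no BMI value to reproduce. Example weights and heights are illustrative. Write w for weight in kg and h for height in cm.

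**Step 1: evaluate the formula.**

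- Reading A, left to right: w / h × h = w.
- Reading B, product as denominator: w / (h × h), in kg/cm².
- Correct: w / (h/100)² = 10,000 × w / (h × h), in kg/m².

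| w (kg) | h (cm) | Reading A | Reading B | Correct | A / correct | Correct / B |
|---|---|---|---|---|---|---|
| 50 | 150 | 50 | 0.00222 | 22.22 | 2.25 | 10,000 |
| 70 | 170 | 70 | 0.00242 | 24.22 | 2.89 | 10,000 |
| 100 | 185 | 100 | 0.00292 | 29.22 | 3.42 | 10,000 |

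Under A the ratio to the correct value is (h/100)², which changes from person to person, so ranks change. Under B it is the same constant for everyone, so ranks do not change.

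**Step 2: the section 9.7.1 models and Table 23.**

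- Reading A: the BMI column equals the weight column. The one-predictor BMI model is the weight model. With intercept, weight and this BMI, the design matrix has rank 2 of 3; with correct BMI it has rank 3.
- Reading B: multiplying a covariate by a constant changes its coefficient and standard error by the same factor, so the test statistic and p-value stay as they were.

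An ordinary least-squares fit to one simulated data set (150 participants, invented outcome) illustrates this:

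| BMI used | Slope | t |
|---|---|---|
| Correct | −0.0421 | −4.87 |
| Reading B | −421.4 | −4.87 |
| Reading A | −0.00917 | −3.34 |

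**Step 3: the median split in section 10.2.1.** The assumptions here are not from the SAP: 150 participants, mean height 168 cm, height SD 7 to 11 cm, height independent of BMI, and lognormal BMI with median 26.5 and log-SD 0.2. The share of participants on different sides of the weight median and the BMI median was simulated.

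It can be checked by hand. Since log w = log BMI + 2 log(h/100), the height term has SD of about 2 × SD/168 on the log scale. For two jointly normal variables the discordant share is arctan(height-term SD / 0.2) / π.

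| Height SD (cm) | Height-term SD | Share by formula | Share simulated |
|---|---|---|---|
| 7 | 0.0833 | arctan(0.417)/π = 12.6% | 12.7% |
| 9 | 0.1071 | arctan(0.536)/π = 15.7% | 15.7% |
| 11 | 0.1310 | arctan(0.655)/π = 18.5% | 18.5% |

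These shares apply to reading A only. Under reading B the simulated share is 0%.

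**Step 4: the primary endpoints.** The safety endpoint (section 9.5.5) and the tolerability endpoint (section 9.6) are proportions of participants with an event, and neither uses BMI. Randomization is stratified by gender and region (section 4.7), not by BMI.

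**The case against.** The best defence is that this is a notation slip. Writing height twice makes sense only as height squared, since nobody sets out to divide by height and multiply it back. The line uses words, whereas the population definitions beside it use database field names. BMI is universally known, and a value of 0.0024 or a BMI column identical to weight would be noticed. On this defence the likely intention is reading B, where ranks and tests survive.

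Much of that stands. It makes reading B the more natural account of what was meant, and it limits the practical harm. It does not make the line correct: reading B still lacks the conversion to metres, and reading A is what the named software does with the expression as printed. A validation programmer who followed the text would either repeat the error or disagree with a correct program, and the SAP gives nothing to settle the difference.

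A reader might infer two stronger conclusions that the document does not support:

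- **That every BMI analysis is wrong.** This holds for reading A only. Under reading B the median split, test statistics and p-values are the same, and the SAP sets no absolute BMI cut-off that a change of scale could break.
- **That the model with all predictors cannot be fitted.** Under reading A the separate BMI and weight effects are not estimable. Software commonly drops the redundant column and still estimates the remaining predictors, and the one-predictor models fit in any case.

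**Conclusion.** The stated derivation is wrong under both readings, and nothing else in the SAP corrects it. The arithmetic is certain; the consequences depend on the reading.

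- **Left to right:** BMI is body weight. The BMI association in section 9.7.1 and Table 23 is a weight association, BMI and weight effects cannot be separated in the joint model, and the SMC table is split by weight. The 13% to 19% misplaced rests wholly on the assumed height and BMI distributions.
- **Product as denominator:** printed BMI values are 10,000 times too small and per-unit coefficients 10,000 times too large. The median split and the tests are unaffected, provided the derived value is kept at full precision.

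The reach is limited to a secondary PK analysis, one SMC table, one final-report table and optional exploratory work. Severity is minor. The SAP does not show which expression was programmed, so it cannot be concluded that any reported result is wrong.

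**What to change.** Replace the Appendix line with: BMI (kg/m²) = weight (kg) / [height (cm)/100]². This supplies the brackets, the conversion and the unit. For 70 kg and 170 cm it gives 70 / 1.70² = 24.22 kg/m².

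The cost is one line of text. No new data are needed, and no analysis method or clinical procedure changes. If any table using BMI has already been produced, check which expression its program used.
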